4.10. Funding source

Planned sources of funding for this study are from internal departmental grants without potential for conflicts-of-interest. No submission for additional funding sources is planned at this time.

5. Anticipated results and potential public health impact

The potential benefit of this study would include knowledge about the success of vitamin D supplementation on various critical care outcomes. While they may not directly apply to a patient, they can be useful to additional critical care patients admitted an ICU in the future. The societal benefit will include reduced patient morbidity and mortality, as well as shorter hospital stays and therefore reduced ICU expenditure. Vitamin D is a relatively cost-effective medication that is well-tolerated. Its potential impact to reduce hospital stays, by even 1 day would play a significant role in reducing patient cost, disease morbidity, and risk from hospitalization. Future research directions can involve a multi-center randomized clinical trial to validate the effect of vitamin D in the neurocritical care patient as well as further molecular studies evaluating the non-skeletal effects of vitamin D. Additional, studies on vitamin D as a biomarker and effects on a cellular level can also be forthcoming if a potential benefit is identified clinically. Identification of the molecular mechanisms by which vitamin D may alter disease pathology may serve as a method for the development of additional treatments.

6. Protocol amendments

6.1. 1/10/17, Addition of phone consents as well as two study co-investigators, [name] and [name] was performed. Repeat vitamin D levels at 3 days following administration of study drug or placebo was modified from prior planned repeat vitamin D at 7 days.

6.2. 8/6/17, Addition of physical therapy assessment and modified Rankin scale as secondary outcomes of the study. Change of study faculty sponsor from [name] to [name] as [name] is leaving the University of Utah.

Table 1: Summary of Study Characteristics	
Title	Randomized Clinical Trial of Hypovitaminosis D Treatment in the Neurocritical Care Unit
Methodology	Randomized, double-blinded, placebo-controlled clinical trial
Study Duration	1-1.5 years (12 months recruitment, 3-6 month analysis)
Study Center(s)	University of Utah Health Sciences Center
Objectives	
 1. Evaluate the impact of vitamin D supplementation on the length-of-stay of emergent neurocritical care patients (primary outcome) 2. Evaluate the impact of vitamin D supplementation on in-hospital mortality, ICU length-of-stay, Glasgow Outcome Score on discharge, complications, and quality-of-life metrics (secondary outcome)
Primary Aims	Length-of-stay
Secondary Aims	ICU length-of stay, in-hospital mortality, 30-day mortality, ICU complications (sepsis, pneumonia, urinary tract infection), Glasgow Outcome Score, medication adverse events , modified Rankin Scale, physical therapy assessments
Number of Subjects	218 per treatment arm, total 436
Intervention	Vitamin D3 540,000 IU oral vs. placebo
Diagnosis and Main Inclusion Criteria	
Patients >18 years of age
 
Patients admitted to the neurosurgery or neurology services
 
Patients admitted to a critical care unit
 
Informed consent
 
Expected to stay in the ICU for 48 hours or more
 
Vitamin D deficiency (<20ng/ml)

Exclusion criteria	
Patients where a vitamin D level was not drawn within 48 hours of admission
 
Patients not randomized within 48 hours of admission
 
Readmitted patients to the critical care unit
 
Lack of informed consent
 
Prior supplementation with vitamin D
 
Severely impaired gastrointestinal function
 
Other trial participation
 
Pregnant or lactating women
 
Hypercalcemia (total calcium of >10.6 mg/dL or ionized serum calcium of >5.4 mg/dL)
 
Tuberculosis history on clinical exam
 
Sarcoidosis history on clinical exam
 
Nephrolithiasis within the prior year
 
Patients not deemed suitable for study participation (ie, psychiatric disease, living remotely from the clinic, or prisoner status)
 
Pregnant or nursing women

Data and safety	Monthly review of data entry

monitoring	Quarterly independent review of data safety metrics Daily review of patient neurological exam, and laboratory values (CBC, BMP, calcium, phosphate) Interim 6-month data analysis
Statistical Methodology	T-test (parametric), Chi-square (non-parametric), univariate regression, multivariate linear regression, logistic regression, Kaplan-Meier survival, Cox proportional hazards modeling, interim analysis SPSS (IBM, Armonk, NY)

Table 2: Demographic, Clinical, and Safety Variables

Demographic Variables

• Name• Medical record number• Date of birth• Gender• Diagnosis• Ethnicity/race
Clinical Variables

• Date of admission to NCCU• Disease category (tumors, trauma, vascular, other)• Disease severity: Glasgow Coma Scale, Simplified Acute Physiology Score II• Medical comorbidities: diabetes, hypertension, heart disease, cancer history• Any surgeries during hospitalization• Randomization – vitamin D or placebo• Vitamin D level on admission• Date vitamin D level• Vitamin D level 3 days post treatment• Date vitamin D level 3 days post treatment• Date ICU discharge• Date hospital discharge• Date deceased• Glasgow Outcome Score on discharge• EQ-5D on discharge• Discharge disposition• Hospital complications (specifically: deep vein thrombosis, bacteremia, urinary tract infection, pneumonia, readmission to NCCU)• Glasgow Outcome Score at 3 and 6 months• EQ-5D at 1, 3 and 6 months• Physical therapy assessments at discharge• Modified Rankin Scale on discharge
Safety Monitoring

• Common Terminology Criteria for Adverse Events (CTAE) V4.0• Daily ICU laboratory studies (CBC, BMP, calcium, phosphate)• Daily neurological exam• Quarterly independent review of safety and data• Monitoring of adverse events

Table S1: Clinical Studies Evaluating Vitamin D in a Critical Care Environment			
Reference	Study type	Participants/ groups	Summary
Van den Berghe 2003	RCT	22 200 IU vs. 500IU	Minimal change in serum markers
Ostermann 2007	Retrospective cohort	100 Normal vs. insufficient vs. deficient	Hospital-free days were significantly different between patients with deficiency and sufficiency No significant relationship between 25(OH)D concentrations and mortality
Lucidarme 2010	Retrospective cohort	100 Normal vs. insufficient vs. deficient vs. undetectable	28-day mortality was significantly different between the four groups No significant association between 25(OH)D concentrations and length of ICU stay. 79% of patients had low 25(OH)D concentrations
Mata-Granados 2010	RCT	33 Placebo vs. 60,000 IU PO, vs. 2mcg IV vit D3	97% of critically ill patients were vitamin D deficient. Group B (60,000 IU) showed a statistically significant increase in 25(OH)D concentrations.
Cecchi 2011	Retrospective cohort	170 Severe sepsis vs. non-septic trauma	28-day mortality was not statically different between the two groups with rates of 27.9% in severe septic patients and 11.1% in trauma patients
Braun 2011	Retrospective cohort	2,399 Normal vs. insufficient vs. deficient	Preadmission 25(OH)D deficiency is associated with mortality Adjusted 30-day morality odds ratio was 1.00, 1.36, and 1.69, respectively
Amrein 2011	RCT	25 Placebo vs. 540,000 IU enteral	The mean serum 25(OH)D increased in the treatment group 25 ng/mL. Deficiency was corrected in 2 days with
Venkatram 2011	Retrospective cohort	437 Normal vs. insufficient vs.	Higher hospital mortality for patients with vitamin D deficiency but not insufficiency

		deficient	
Braun 2012a	Retrospective cohort	1,325 Normal vs. insufficient vs. deficient	Adjusted 30-day mortality odds ratio was 1.00, 1.35, and 1.94 b respectively
Braun 2012b	Retrospective cohort	2,075 Normal vs. insufficient vs. deficient	Adjusted 30-day mortality odds ratio was 1.00, 1.41, and 1.61, respectively Preadmission 25(OH)D deficiency is significantly associated with acute kidney injury
Arnson 2012	Prospective cohort	130 Normal vs. insufficient	Mortality was lower for vitamin D deficient patients (15±12.4 days vs. 24.2 ± 16.5 days) Vitamin D levels correlated with WBC count
Flynn 2012	Prospective cohort	66 Normal vs. deficient	Longer length of stay, infection rates and rates of sepsis in patients with vitamin D deficiency
Higgins 2012	Prospective cohort	196 Normal vs. deficient vs. insufficient	Vitamin D levels decreased 3 days after admission and remained through 10 days Higher vitamin D levels were associated with shorter time to ICU discharge (HR 2.11) Vitamin D not associated with mortality or infection rate
Nair 2012	Prospective cohort	100 Normal vs. deficient vs. insufficient	Vitamin D deficiency associated with fewer hospital-free days. Secondary hyperparathyroidism was highly prevalent in the critically ill population
Rommelts 2012	Prospective cohort	272 Normal vs. deficient vs. insufficient	Vitamin D deficiency associated with increased risk of ICU admission and 30-day mortality in patients with community-acquired pneumonia
Nair 2013	Retrospective cohort, RCT	196 Normal vs. insufficient vs. deficient Placebo vs. low (200IU) vs. high (500IU) supplement	Mean time-to-alive at ICU discharge was 5.9 ± 5.4, 6.8 ± 6.0, and 10.6 ± 8.4 respectively 25(OH)D insufficiency was not associated with mortality 25(OH)D levels were higher in the high dose group on days 2, 6, and 7. Doses studied did not

			normalize 25(OH)D serum concentrations
Aygenel 2013	Prospective cohort	201	Increased mortality in vitamin D deficient (<20ng/mL) patients (43 vs. 26%) Increase rates of severe acute disease, worsened laboratory studies on admission, morbidity and exposure to invasive therapy in deficient patients.
Su 2013	Prospective cohort	206 (105 ICU) Normal vs. ICU sepsis	Lower vitamin D seen in patients with ICU sepsis compared to normal patients No difference in mortality with vitamin D levels
Amrein 2014	RCT	475, (patients with deficiency ≤ 20 ng/ml) Placebo vs. 540,000 IU x1, monthly 90,000 IU for 5 month	No difference in mean hospital stay (19.3 vs. 20.1), hospital mortality (35.3% vs. 28.3%), 6-month mortality (42.9% vs. 35.0%) Severe vitamin D subgroup (n=200) showed no difference in hospital stay (19 vs 20.1 days) and 6-month mortality (50% vs. 34.7%) Severe vitamin D subgroup showed significantly lower hospital mortality (46.1% vs. 28.6%, p=0.04),
Moromizato 2014	Retrospective cohort, two-center	3,386 Normal vs. insufficiency vs. deficiency	Preadmission vitamin D deficiency was predictive for risk of sepsis including after adjustment for other variables 90-day mortality was 1.6x higher in patients with preadmission vitamin D insufficiency and deficiency (HR. 1.63)
Dickerson 2015	Retrospective cohort	65 50,000 IU qweek, Blweek, Tlweek for 4 weeks	Normal vitamin D levels achieved in 6%, 11% and 26% of patients
Brook 2015	Retrospective cohort	300 Normal vs. deficient	Vitamin D levels showed an inverse correlation with non-home discharge destination
Nair 2015	RCT	50 150,000 IU vs.	65% vs. 67% of patients normalized vitamin D levels by 7

		300,000 IU vitamin D3 IM	days 80% vs. 83% of patients normalized vitamin D levels by 14 days Secondary hyperparathyroidism manifest in 25% of patients
Alizadeh 2015	Retrospective cohort	70 Normal vs. deficient	Longer length of stay (7.8 vs. 4.05 days) with deficient patients but no difference in hospital mortality
Quraishi 2015	RCT	30 Placebo vs. 200,000 IU cholecalciferol vs. 400,000 IU cholecalciferol	Plasma levels of vitamin D peaked on day 5 of treatment CRP levels did not differ between groups
Verceles 2015	Retrospective cohort	183 Normal vs. deficient	Deficiency was common (61% patients) and not associated with days to wean from ventilation

[figure not shown]

Figure S1: Forest plot of 30-day mortality in studies with univariate analysis of vitamin D sufficiency vs. deficiency. Adapted from de Haan et al. 2014.

[figure not shown]

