2. Background/Rationale

Hypovitaminosis D has a high prevalence among the general population, with some studies showing over half of the elderly population being affected (Chapuy 1997). Among critically ill patients, various studies have shown associations between hypovitaminosis D and multiple negative outcomes including mortality (De Haan 2014,

Rech 2014), ARDS (Dancer 2015), and infection (Flynn 2012). Vitamin D deficiency has also been shown to have impacts on various neurological diseases such as stroke (Yalbuздag 2015, Chung 2015), and dementia (Littlejohns 2014). While the mechanism between vitamin D deficiency and these diseases is not entirely known, evidence suggest that vitamin D can affect vascular reactivity, inflammation, and the immune system (Carthy 1989, Vargas-Vasserot 2011) (Table S1, Figure S1-2).

Vitamin D has been shown to impact prognosis in a variety of retrospective and randomized clinical trials within an intensive care unit (ICU) environment (Amrein 2011). **Despite these findings, there have been no studies examining the impact of hypovitaminosis D in specialized neurocritical care units (NCCU).** Given the often significant differences in the management of patients in NCCU and more generalized intensive care units (Kurtz 2011) there is a need for further inquiries into the impact of low vitamin D levels in this specific environment. **This study proposes a randomized, double-blinded, placebo-controlled, single center evaluation of vitamin D supplementation in the emergent NCCU patient population (Table 1).** We have previously conducted a prospective, observational analysis of 823 NCCU patients and shown a significant reduction in hospital length-of-stay for all patients (7.14 vs. 5.97 days, $p=0.0018$) and for emergent cases (8.21 vs. 6.36 days, $p=0.038$), as well as reduced in-hospital mortality for emergent patients with non-deficient vitamin D levels (26/203 vs. 22/321, $p=0.021$). Nevertheless, these results remain limited in being observational studies without randomization or controls.

3. Study purposes and objectives

1. Evaluate the impact of vitamin D supplementation on the length-of-stay of emergent neurocritical care patients (primary outcome)
2. Evaluate the impact of vitamin D supplementation on in-hospital mortality, ICU length-of-stay, Glasgow Outcome Score on discharge, complications, and quality-of-life metrics (secondary outcome)

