4.2. Exclusion criteria

- Patients where a vitamin D level was not drawn within 48 hours of admission
- Patients not randomized within 48 hours of admission
- Readmitted patients to the critical care unit
- Lack of informed consent

- Prior supplementation with vitamin D
- Severely impaired gastrointestinal function
- Other trial participation
- Pregnant or lactating women
- Hypercalcemia (total calcium of >10.6 mg/dL or ionized serum calcium of >5.4 mg/dL)
- Tuberculosis history or clinical exam
- Sarcoidosis history or clinical exam
- Nephrolithiasis within the prior year
- Patients not deemed suitable for study participation (ie, psychiatric disease, living remotely from the clinic, or prisoner status)
- Pregnant or nursing women

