4.3. General protocol

1. Patients will be identified through primary treatment teams, including the Departments of Neurosurgery and Neurology, and through screening of the electronic medical record for patients admitted to the NCCU at the University of Utah Health Sciences Center. Patients admitted for non-elective indications as outlined in the inclusion criteria will be enrolled. The full inclusion and exclusion criteria are listed in Table 1. We expect most patients to be admitted to the neurosurgery service and NCCU.
2. A Vitamin D level will be drawn on all non-electively admitted NCCU patients as part of our standard admission protocol.
3. Patients with a Vitamin D level <20ng/ml, defined as deficient, will be consented for the trial. Patients that do not consent for the trial will be studied retrospectively as part of our standard-of-care similarly to our previous prospective trial. Women between 18-45 years of age will undergo a serum or urine pregnancy test to rule out pregnancy prior to enrollment.
4. Patients will be randomized 1:1 to receive Cholecalciferol (Vitamin D3, 540,000 IU once orally or by feeding) immediately or placebo by random number generator. Treatments will be blinded to the patient and physician care teams. Placebos will include similar tablets or liquid formulations that mimic the treatment drug but are indistinguishable.
5. A subsequent Vitamin D level will be drawn 3 days after drug administration or on date of discharge if sooner than 3 days to evaluate the adequacy of vitamin D repletion.
6. Primary outcomes will total hospital length-of-stay. Secondary outcomes will include in-hospital mortality, ICU length-of-stay, ICU complications (rates of sepsis/bacteremia, pneumonia, urinary tract infection), discharge Glasgow Outcome Score, medication adverse events, and quality-of-life metrics. Various patient demographic data will be acquired.
7. Subsequent 30-day mortality will be measured on standard clinical follow-up.

8. 1, 3 month and 6 month Glasgow Outcome Scores and quality-of-life metrics will be obtained. Physical therapy gait distance measurements as well as modified Rankin scale on discharge will be obtained.

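### The infection-complication outcome in section 4.3 and Table 1 cannot be derived from the Table 2 variables: no sepsis item, no complication onset date, no randomization or dosing date

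*Combined protocol and SAP*

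**What the plan says.** The outcome appears in four places.

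- Section 3, objective 2 (repeated in the Objectives row of Table 1) lists "in-hospital mortality, ICU length-of-stay, Glasgow Outcome Score on discharge, complications, and quality-of-life metrics (secondary outcome". Complications are not defined and have no window.
- Section 4.3, item 6: "ICU complications (rates of sepsis/bacteremia, pneumonia, urinary tract infection".
- Table 1, Secondary Aims: "ICU complications (sepsis, pneumonia, urinary tract infection".
- Table 2, Clinical Variables, which section 4.9 cites as the variables to be collected: "Hospital complications (specifically: deep vein thrombosis, bacteremia, urinary tract infection, pneumonia, readmission to NCCU".

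On timing, section 4.2 excludes "Patients not randomized within 48 hours of admission", and section 4.3, item 4 has patients receive "540,000 IU once orally or by feeding) immediately or placebo by random number generator". Table 2's dates run from "Date of admission to NCCU" through ICU discharge to "Date hospital discharge", with the date of death and the dates of the two vitamin D draws. It lists no date for any complication, for randomization or for dosing. Apart from tuberculosis, no exclusion criterion concerns infection, and infection status at entry is not a listed variable. Section 4.9 leaves the analysis of secondary outcomes open and gives no rule for which events count.

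**The concern.** A secondary outcome should be derivable from the data that the plan says it will collect. Here the outcome is named as an ICU event rate in two places and collected under a hospital label in a third, with a different list of components and no dates. Two consequences follow. First, the analyst would have to choose after the fact what sepsis means and which events belong to the ICU. Second, patients are emergent admissions who may be randomized as late as 48 hours after arrival, so some may already have pneumonia, a urinary tract infection or bacteremia at that point. Treatment cannot prevent those events. If they enter the count they add noise to both arms and pull the observed relative risk toward 1. This outcome is also among those closest to the immune and infection rationale in the Background.

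**Working it through.** **Step 1. Components side by side.**

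| Item | Section 4.3 | Table 1 | Table 2 |
|---|---|---|---|
| Label | ICU | ICU | Hospital |
| Sepsis | paired with bacteremia | yes | no |
| Bacteremia | paired with sepsis | no | yes |
| Pneumonia | yes | yes | yes |
| Urinary tract infection | yes | yes | yes |
| Deep vein thrombosis, NCCU readmission | no | no | yes |
| Onset date | – | – | none |

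Table 2 matches section 4.3 in part, through bacteremia. The clean mismatch on sepsis is with Table 1, which names sepsis alone. Nowhere is sepsis defined or bacteremia said to stand for it. Neither logged amendment in section 6 touches this outcome.

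**Step 2. Can an ICU event be identified?** That needs an event date to set against the ICU admission and discharge dates, or a location field. Table 2 has the ICU dates but neither of the others. An undated event cannot be placed in the ICU or on the ward.

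**Step 3. Can a pre-randomization event be identified?** That needs an onset date and a randomization or dosing date. Neither is listed. The day of dosing could often be inferred from the date of the repeat vitamin D draw, planned 3 days after dosing or at discharge if sooner, but without an onset date this does not help.

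**Step 4. What dilution could cost.** The plan states no infection rate and no power for this outcome, so there is no figure to reproduce. All rates below are assumptions.

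- Control patients with a recorded infection: 30% (assumed).
- True relative risk for infections after randomization: 0.60 (assumed).
- q, the share of control infections that began before randomization: 5%, 15% or 30% (assumed).
- n = 198 per arm (section 4.9, the number before the dropout allowance); two-sided 5% (assumed for this outcome).
- One recorded infection per patient; pre-randomization infections equal in both arms.

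All events: control risk 0.30, treated risk 0.30 × [q + (1 − q) × 0.60].
Later onsets only: control risk 0.30 × (1 − q), treated risk 0.60 times that.
Power = Φ{(d − 1.96 × SE0) / SE1}, with d the difference in risks, SE0 = √[2p̄(1 − p̄)/n], p̄ the mean of the two risks, and SE1 = √[(p0(1 − p0) + p1(1 − p1))/n].

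For q = 15%, all events: risks 0.300 and 0.198, d = 0.102, SE0 = 0.0435, SE1 = 0.0432, power = Φ(0.39) = 65%. Later onsets only: risks 0.255 and 0.153, d = 0.102 again, SE0 = 0.0405, SE1 = 0.0402, power = Φ(0.56) = 71%.

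| q | Observed relative risk, all events | Power, all events | Power, later onsets only |
|---|---|---|---|
| 5% | 0.62 | 76% | 77% |
| 15% | 0.66 | 65% | 71% |
| 30% | 0.72 | 48% | 61% |

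The absolute difference is the same under both counts, so the fix gains only by removing noise. With no pre-randomization infections, power would be 80%. The fall from 80% to the last column reflects fewer preventable events, and no counting rule recovers it.

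**The case against.** Several points on the other side are sound.

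- **Sepsis.** Section 4.3 writes sepsis and bacteremia as one item. The investigators may regard them as a single endpoint, shortened in Table 1. That is possible, but it is not stated. Culture-negative sepsis would then be missed, and the three wordings still need reconciling.
- **Pre-dose infections.** A reader might infer that infections present before dosing are counted as outcomes. The documents do not say so. They neither include nor exclude such events, and a presenting disease such as meningitis would go under the separate diagnosis field and need not be called a complication. What stands is that these events could be counted and cannot be separated using the listed variables.
- **Window.** A reader might also infer that complications are counted over the whole hospital stay. That rests only on the label in Table 2, which may simply head a wider list. No start or end of the window is given anywhere.
- **Recoverability.** Table 2 is a variable list, not a case report form. It includes the medical record number, and adverse events are monitored separately. Dates might be recovered from the chart. The criticism is therefore that they are not specified, not that the data are lost.
- **Importance.** The trial is sized on length of stay and claims no power for infections. Blinded randomization balances earlier infections on average, so neither bias toward an arm nor inflated false-positive error is expected.

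**Conclusion.** The concern holds as a conflict between a stated secondary outcome and the variables listed for it. Following Table 2 as written, Table 1's sepsis outcome and the ICU-specific rates in section 4.3 and Table 1 cannot be derived, and earlier infections cannot be separated from later ones. This part rests on the text alone and is firm.

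The size of the dilution is not firm. Under the assumed rates, counting all events costs about 2, 6 or 13 percentage points of power for earlier-onset shares of 5%, 15% or 30%. A weaker effect shrinks the gap: with a relative risk of 0.80, a 15% share and the full 218 per arm, power is 22% against 24%. These figures illustrate direction and scale only. The primary outcome is not affected. The correction is worth making because the outcome is named in the plan and the remedy is cheap.

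**What to change.** 1. Use one definition and one stated window, either ICU stay or hospital stay, in section 4.3, Table 1 and Table 2.
2. Either list sepsis in Table 2 with diagnostic criteria, or drop it from section 4.3 and Table 1 in favour of bacteremia.
3. Add to Table 2 the date and time of randomization and of dosing, infection status at randomization, and the onset date and location (ICU or ward) of each complication.
4. Count as outcomes only events with onset after randomization, and treat earlier infections as a baseline variable. Starting the window at randomization, not at drug administration, keeps randomized but undosed patients in the comparison. State how a new infection is handled in a patient who already had one at baseline.

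The cost is a few more fields abstracted from the chart, with no extra visits or procedures. Reported complication rates will be lower: in the illustration the control rate of 30% becomes 28.5%, 25.5% or 21% for earlier-onset shares of 5%, 15% or 30%.
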